13. CORRELATIVE STUDIES

The correlative studies described below will be performed in liposarcoma patients only.

13.1 Proteomics studies

Introduction

Reverse phase protein array (RPPA) is a functional proteomics technology capable of profiling protein levels and post-translational modifications, including phosphorylation, across various biological specimens, including human tissue, using a miniaturized analyte-down dot-blot immunoassay. The technique allows for monitoring of protein expression across a large number of samples in a quantitative, high-throughput and cost-effective manner not currently matched by other proteomics technologies.

In RPPA, analytes are immobilized on a solid phase, most often nitrocellulose, and probed with an affinity reagent, usually a high-affinity validated antibody. The technology is particularly well suited for profiling the state of cell signaling networks owing to small sample requirements, high sensitivity in the picomolar range and precision as demonstrated by coefficient of variance < 15%. RPPA has been used in a range of preclinical and clinic research applications for identification of novel therapeutic targets and predictive biomarkers, pharmacodynamic analysis and monitoring of therapeutic response.²⁷

We aim to employ RPPA to analyze changes in total and phosphoprotein RTKs between baseline and on-treatment tumor biopsy specimens in order to demonstrate pharmacodynamic evidence of on-target activity by MGCD516, evaluate drug effects on activation/suppression of downstream signaling pathway components and assess for possible compensatory upregulation of alternative RTKs and signaling pathway components as a mechanism of acquired resistance. Specifically, we will study changes in total and phosphoprotein levels for the following proteins: 4E-BP1, Akt, AXL, EGFR, Eph family, ERK 1/2, FGFR2, IGF1-R, KIT, MEK 1/2, MET, p70 S6 kinase, RET, RYK, PDGFRa, PDGFRb and VEGFR1-2. Significant changes in total and phosphoRTKs will then be confirmed by Western Blot.

Prior Clinical Studies Employing RPPA

RPPA has been employed as a component of numerous clinical trials for a similar purpose, demonstrating the feasibility of this method in human tumor specimens obtained in a clinical trial setting. One of the earliest clinical trials to employ RPPA was a phase II trial of gefitinib in patients with refractory or recurrent epithelial ovarian cancer²⁸. Core needle tumor biopsies were obtained before treatment and after 4 weeks on drug, and RPPA was used to characterize expression of total and phosphorylated EGFR, AKT and ERK in microdissected tumor specimens. The majority of patients demonstrated changes in EGFR and pEGFR although no clinical benefit was noted for the drug. There was a trend for increased toxicity with greater changes in phosphorylation of EGFR, ERK and AKT. The same group later carried out a phase II trial of vandetanib, a small molecule inhibitor of VEGFR2 and EGFR, in platinum-resistant ovarian cancer patients. Core needle biopsies were obtained at baseline and after 6 weeks on treatment. RPPA was then used to assess multiple RTK and signaling pathway component endpoints in the paired tissue biopsy specimens. The study used a Simon II stage design, and the drug failed to demonstrate sufficient clinical efficacy in the first stage. Interestingly, however, RPPA suggested potential reasons for the drug's lack of efficacy. A reduction in EGFR activation and downstream pAKT was demonstrated by RPPA but, despite measurable levels of total and activated VEGFR2 at baseline, no modulation of that target was seen across any of the paired biopsies. This was corroborated further by lack of significant changes in circulating VEGF levels in plasma.

In another study, RPPA was used in preclinical models (cell lines and xenografts) treated with the selective AKT inhibitor GDC-0068 to identify evidence of signaling pathway modulation with this drug²⁹. Potential biomarkers were then analyzed in patient samples treated with the drug. Pharmacodynamic evidence of AKT inhibition was demonstrated in human tumor specimens at clinically achievable doses and the degree of biomarker inhibition correlated to tumor growth inhibition in preclinical models. Moreover, in both the preclinical and clinical samples, compensatory feedback activation of ERK and HER3 was observed using RPPA thereby identifying possible candidates for combination therapy to optimize use of the novel drug.

RPPA has also been employed in numerous clinical trials in breast cancer. Based on preclinical data showing that rapamycin synergistically enhances the cytotoxicity of paclitaxel in triple negative breast cancer, a randomized phase II trial was conducted in 50 patients evaluating

neoadjuvant chemotherapy with or without everolimus³⁰. RPPA was used to measure molecular changes in the PI3K/Akt/mTOR pathway at baseline and at 48 hours and after surgery. These measurements were the primary endpoint of this clinical trial. Phosphorylation of ribosomal pS6 was significantly decreased in patients treated in the everolimus arm at 48 hours as shown by RPPA. A separate phase II breast cancer study randomized HER2 positive stage II or III breast cancer patients to trastuzumab, lapatinib or both agents with chemotherapy³¹. Core needle biopsies were obtained for RPPA analysis at baseline and after 2 weeks of anti-HER2 therapy. The study demonstrated a correlation between pathologic complete response at surgery and several protein biomarkers identified by RPPA. Mean expression levels of pEGFR Tyr1068 at baseline predicted response in the lapatinib treated patients. Across all treatment arms, the ratio of pTEN to pFOXO, and PI3K to pFOXO, correlated to likelihood of pathologic complete response.

Tissue Procurement and Handling

A subset of liposarcoma patients will participate in this correlative study with a target sample size of 10 patients. The first 10 liposarcoma patients enrolled on the study (beginning with the first patient enrolled in stage I) with tissue suitable for biopsy will participate, regardless of the site at which the patient is accrued. If the study fails in stage I and proceeds to the exploratory cohort of various tumors, no further RPPA analyses will be performed. However, if the study proceeds to stage 2 in liposarcoma, and additional patients are needed to reach a total sample size of 10 for this correlative, further liposarcoma patients will participate to accrue a total of 10 liposarcoma patients with paired tissue biopsies.

Paired (pre-treatment and on-treatment) core biopsy specimens will be obtained. The baseline biopsy specimen will be obtained at any point between day -14 and the date of first treatment with the study drug (cycle 1, day 1) provided consent is obtained and the other eligibility criteria for the study are met. The on-treatment biopsy specimen will be performed with a target timepoint of cycle 1 day 15 (with a window of cycle 1 days 15 through 20).

The same tumor lesion should be biopsied at both time points whenever possible. Specimens are obtained using a 16-18 gauge core needle under imaging guidance by an interventional radiologist at the treating institution. At least 4 cores are obtained, and up to 6-8 cores if feasible (with safety of the procedure prioritized in all cases). The first 4 cores are placed in FFPE and the subsequent 2-4 cores are cryopreserved and flash frozen. From the FFPE material, an H&E section should be cut for confirmation/diagnostic purposes, to be reviewed at the institution collecting the sample as per standard of care. These following specifications apply:

- (1) A 16 to 18 gauge needle is satisfactory;
- (2) Time from core needle biopsy (CNB) removal to initiation of fixation should be \leq 30 min;
- (3) CNB material should be immersed in sufficient volume of 10% neutral buffered formalin to ensure adequate fixation (>15 to 20 times greater than estimated volume of CNB);
- (4) Formalin fixation to last between 6-72 hours at room temperature; and after fixation, proceed

to paraffin embedding. Tissue blocks should be stored at ambient conditions.

(5) Material should be labeled, accessioned and stored consistent with standard of care policies and procedures at the participating institution.

Disposition of FFPE tissue:

Following the biopsy, material will be accessioned to the pathology department at the institution obtaining the material as per institutional standard of care guidelines. FFPE tissue blocks should be stored at ambient conditions. Once all samples have been obtained and only when directed by the investigators, sections from the pre-treatment and on-treatment biopsies for all study participants will be made as described below, appropriately labeled, and sent to Theralink Technologies where RPPA studies will be performed. Specifically, the following steps will be taken:

- (1) Since tissue sections that are older than 6 weeks should not be used for RPPA analysis, prepared tissue sections should be prepared and shipped within 2 weeks to allow for transportation and on-site sample preparation before the 6 week expiration date. Thus this process should only be initiated when directed by the investigators.
- (2) The initial, uppermost tissue section that had been exposed to air should either be discarded, or used for a non-RPPA purpose such as H&E staining.
- (3) Six (6) sections should be prepared to a five (5) μm thickness and air-dried at room temperature. **Do not bake.** Alternatively, five (5) tissue sections and one (1) H&E-stained tissue section can also be supplied. Sections should be mounted onto either FisherbrandTM SuperfrostTM ExcellTM Microscope Slides (cat# 22-037-247); or uncharged slides with no adhesives/treatment (e.g. poly-L-lysine). Each slide should be labeled with the study participant identification number and the timing of the biopsy (e.g. baseline/pre-treatment or on-treatment). This information will be provided by the clinical research team.
- (4) FFPE samples should be shipped with cold packs to Theralink Technologies, Inc. at the address shown below. Please provide notification of all incoming shipments to include the name of the courier, tracking number for the shipment, and expected date of delivery to [name] via e-mail to: [contact].

Theralink Technologies, Inc. [name] ATTENTION: [name] [contact] Unused FFPE material will be returned to the sending institution.

Disposition of flash frozen tissue:

Cryogenic vials for flash frozen tissue should be labeled with the study number, study-assigned patient identification number, patient date of birth, and date and time at which the specimen was acquired. This tissue should be immediately placed into the labeled cryogenic vials. Tumor cores should be frozen individually in separate cryovials, as collected, in order to minimize the time between removal and freezing. Vials with tissue should be placed in liquid nitrogen for 2 minutes or longer until frozen solid. If obtained at CUMC, flash frozen tissue should be placed on dry ice and brought by a member of the clinical research team directly to the laboratory of [name] where the material will be stored at -80°C until ready for further analyses. If obtained at a study site other than CUMC, the material should be stored at -80°C and, at the earliest convenience, packed on dry ice and sent by overnight shipping to the laboratory of [name] by Federal Express or UPS with anticipated delivery on a Monday through Friday from 9 am to 4 pm, excluding holidays (procedures should be scheduled if necessary to accommodate shipping on this timeline). Samples can be sent to:

[name]

Attention: MGCD516 Study
Herbert Irving Comprehensive Cancer Center
Columbia University Medical Center
[name]
[name]

Regardless of the site at which the biopsy is obtained, an e-mail should be sent to [contact] at least 24 hours in advance to alert the laboratory to expect the arrival of a sample. All labeled flash frozen samples will be stored at -80°C in the laboratory of [name] until such time as relevant correlative studies are performed.

Analytic Procedures

RPPA Tissue Study Procedures:

The following procedures and analysis will be performed by Theralink Technologies, Inc.. Sections are analyzed for adequacy by a pathologist and specimens with predominant necrosis or lymphocytic infiltration are not used. Tumor cells and/or stromal cells are microdissected using an Arcturus PixCell IIe (Invitrogen, Life Technologies, Grand Island, NY). Microdissected cells are stored at -80C prior to reverse phase protein microarray printing. Microdissected cells are subject to lysis with a 10% (v/v) solution of Tris(2-carboxyethyl) phosphine (Pierce, Rockford, IL) or a 2.5% solution of 2- mercaptioethanol (Sigma) in Tissue Protein Extraction Reagent (T-PERTM, Pierce)/Tris-glycine 2X SDS buffer (Invitrogen). Cell lysates are stored at -80C prior to microarray construction.

Cellular lysates are printed on glass backed nitrocellulose array slides (FAST Slides, Whatman,

Florham Park, NJ) using an Aushon 2470 arrayer (Aushon BioSystems, Burlington, MA) equipped with 350-µm pins. Each array consists of microdissected tumor samples. The before/after pair for each patient are printed on the same array for most specimens. Samples are printed in duplicate in 4-point or 2-point dilution curves. Immunostaining is performed on a Dako Autostainer per manufacturer's instructions (CSA kit, Dako, Carpinteria, CA). Each slide is incubated with a single primary antibody at room temperature for 30 minutes. Reverse phase protein microarray analysis of phosphorylated/total protein endpoints is then conducted for the RTK targets described in section 13.1.1. Antibodies were validated by Western blotting. The negative control slide is incubated with antibody diluent as a substitute for the primary antibody. Secondary antibody is goat anti-rabbit IgG H+L (1:7,500) (Vector Labs, Burlingame, CA) or rabbit antimouse IgG (1:10) (Dako). Subsequent signal detection is amplified via horseradish peroxidase mediated biotinyl tyramide deposition with chromogenic detection per manufacturer's instructions (Dako). Array slides are scanned at 600dpi on a flatbed scanner (UMAX PowerLook) and saved in a tiff format (Adobe Photoshop). Spot intensity is analyzed using ImageQuant ver 5.2 (GE Healthcare). Total protein per microarray spot is determined with a Sypro Ruby protein stain (Invitrogen/Molecular Probes) per manufacturer's directions and imaged with a CCD camera (NovaRay, Alpha Innotech, San Leandro, CA).

Data compilation is performed with proprietary software for background correction and normalization. The mean local area background of each spot is used to assess spot intensity values greater than 2 S.D. above background. Replicate values are averaged. If the CV between replicates is >20%, the spot is flagged and a value of "CV too high" reported. Signal intensity from the secondary antibody alone (negative control) slide is subtracted from the signal intensity of the primary antibody slide. Each patient analyte sample is normalized to the corresponding Beta actin value. Total protein is analyzed as a quality control marker for each microarray spot. Total protein per spot is quantified as a means to assess overall sample and printing quality. Low total protein levels indicate inadequate sample quality or quantity. The results of the analysis will be reported to the study coordinators at CUMC along with the patient's identification number and date of birth and subsequently will be added to the case report form and appropriate files. Unused tissue will be returned by Theralink Technologies, Inc. to the institution which performed the procedure to obtain them.

Western Blot Procedures:

These studies will be performed in the laboratory of [name] at CUMC. We will attempt to confirm RPPA findings by assessing changes in total and phosphorylated MET, IGF1-R and PDGFRb (RTKs identified as important for LPS proliferation in preclinical studies) by Western blot in the pre-treatment and post-treatment tumor biopsy specimens. Assessment of these targets in pre-treatment biopsies will also serve to evaluate whether phosphorylated expression of these targets demonstrated in cell lines is recapitulated in human tissue. We will also use Western blot to validate changes in other RTKs in which significant changes were identified by the RPPA analysis if available tissue permits. Briefly, protein extractions are prepared using a radio immunoprecipitation assay lysis buffer. Protein concentrations are measured using the BioRad protein assay and equal amounts loaded onto gradient gels. Membranes are probed with primary antibodies and bound antibodies are then detected with horseradish peroxidase and visualized by enhanced chemiluminescence reagents. Validated

antibodies for MET, IGF1-R and PDGFRb are obtained from Cell Signaling Technology. Unused tissue will be returned by CUMC to the institution which performed the procedure to obtain them. If the tissue was obtained at CUMC, the tissue will be sent for archival in the Department of Pathology using the patient's name and medical record number.

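### RPPA slides show the biopsy time point, so specimen rejection and microdissection are done unmasked; a neutral code would remove this cheaply

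*Combined protocol and SAP*

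**What the plan says.** Section 13.1, Disposition of FFPE tissue, has sections cut from the baseline and on-treatment biopsies of all participants in one step, when the investigators direct it, and shipped to an outside laboratory. Step 3 sets the label: "Each slide should be labeled with the study participant identification number and the timing of the biopsy". The example given is "e.g. baseline/pre-treatment or on-treatment", and the text adds: "This information will be provided by the clinical research team".

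Under RPPA Tissue Study Procedures the same section states: "The following procedures and analysis will be performed by Theralink Technologies, Inc". The first of these procedures is: "Sections are analyzed for adequacy by a pathologist and specimens with predominant necrosis or lymphocytic infiltration are not used". Microdissection follows, and the text allows tumor cells, stromal cells or both. Lysis, printing, automated staining, scanning and software-based intensity measurement come after that.

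Frozen cores for the Western blot are labeled at collection with, among other items, "patient date of birth, and date and time at which the specimen was acquired". The blots are run at the coordinating center.

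Section 15.5.1 tests, protein by protein, whether the paired change from baseline differs from zero (paired t-test, or Wilcoxon signed-rank if the data are not normal) in a subset of 10 liposarcoma patients, with exploratory intent.

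**The concern.** The label tells the laboratory which slide is which before anyone decides whether a specimen is usable or which cells to take from it. Both decisions determine what tissue is measured, and neither is tied to a numeric rule. A pathologist or operator who knows the time point may, without intending to, accept or dissect on-treatment tissue differently from baseline tissue.

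In a trial with a control arm, such a difference would tend to occur in both arms and cancel. Here there is no control arm, and section 13.1 intends the change to be read as evidence that the drug hits its targets. What is at stake is the credibility of that pharmacodynamic reading.

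**Working it through.** The plan states no alpha, standard deviation, effect size or power for the RPPA comparison, so there is no figure to reproduce. The check is to set the relevant text side by side.

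1. **Is the time point visible?** Yes. Step 3 of section 13.1 requires it in plain words, supplied by the clinical research team before shipment.

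2. **Is it masked anywhere?** Not in the text. Section 10.8 (blinding of study drug) and section 12.8 (unblinding procedures) both say the topic does not apply, and 10.8 concerns the drug. Sections 13.1 and 15.5.1 mention no recoding on receipt, no masked pathologist or operator and no randomized processing order.

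3. **Which later steps need judgement?**
   - *Adequacy review.* The ground for rejection is that "specimens with predominant necrosis or lymphocytic infiltration are not used". No cut-off defines predominance. Rejecting either member of a pair removes that patient from the paired test, which is 1/10 = 10% of the target sample.
   - *Microdissection.* The choice between tumor, stroma or both is left open, with no rule that it be the same for both members of a pair.

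4. **Which later steps do not?** Staining is by autostainer. Intensity is read by scanner and software. Background and negative-control signal are subtracted, replicates with a CV above 20% are flagged, and values are normalized to beta-actin. None of these depends on the time point as written.

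5. **Can the analysis separate handling from drug?** Write the observed change in patient i as D_i = δ + h + e_i, where δ is the drug effect, h is any average difference in handling between on-treatment and baseline tissue, and e_i is noise with mean zero. The mean change then estimates δ + h. The test in section 15.5.1 asks whether δ + h = 0. With no control pairs there is no separate estimate of h, so the design cannot remove it. Masking acts on h directly.

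6. **Does the laboratory need the time point?** Section 13.1 has most pairs printed on one array. That requires knowing which two samples belong together, not which came first. A within-patient code keeps the pairing.

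**The case against.** The strongest reply is that the route is narrow and the endpoint minor. Rejection and dissection happen before staining, so nobody can pick cells by their protein signal; what knowledge of the time point could alter is the tissue mix. Measurement is then largely automated. Cutting all sections in one directed step and printing most pairs on one array limit other before/after differences. The laboratory may also recode slides under an unwritten procedure. All of this stands, and it is why the point carries little weight. It does not remove the point, since automated reading cannot undo a selection already made.

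Some stronger readings are tempting, but the documents do not support them.

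- **An inflated error rate of known size.** Assume 10 pairs, a two-sided 5% level (not stated in the plan) and no drug effect. A handling shift of d standard deviations of the paired differences gives a noncentral t with 9 degrees of freedom and noncentrality d√10. For d = 0.10, 0.25, 0.50 and 0.75 the false-positive rate per protein is 5.9%, 10.9%, 29.3% and 56.2%. This range only reflects the assumed d; the documents offer no value for d. Nor can one shift be applied to every protein, because any part shared with beta-actin would cancel on normalization.
- **The dilution series as a biased choice.** The text says "Samples are printed in duplicate in 4-point or 2-point dilution curves", but nothing indicates that the choice depends on the time point or would push normalized values one way.
- **Selective repetition of assays.** No repeat runs are described; a high-CV spot is flagged and reported as such.
- **The Western blot as no protection.** It uses separate frozen cores and equal protein loading, and the text describes no rejection or dissection step of the RPPA kind. It is therefore a partial check on the very route in question. Two limits remain. Frozen cores are those taken after the first four, so they exist only where more than four were obtained. The vial dates also show the order within a pair, although the documents do not say whether the person reading the blot sees them.

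**Conclusion.** The point holds in a limited form. As written, the plan has adequacy rejection and the choice of cells for microdissection made with the time point in view, in an uncontrolled within-patient comparison of about 10 patients. The conclusion rests on the text alone and assumes that the laboratory does not recode slides under a procedure the documents do not mention. The size of any bias is unknown and cannot be derived from the documents. The endpoint is declared exploratory and has no bearing on the 12-week progression-free rate or the stage 1 rule. Severity is low; the case for acting is that the remedy costs little.

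**What to change.** In section 13.1, Disposition of FFPE tissue, step 3, replace the biopsy timing with the participant ID plus a code, A or B, assigned at random within each patient. The clinical research team, which already supplies the label information, would issue the codes when sections are cut. The slide should carry no biopsy date. The key should be held by someone not involved in the assays, for example the study statistician, and opened only after adequacy decisions and normalized values are locked. After unmasking, report rejected specimens by time point.

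Where practical, apply the same codes to the frozen samples before Western blotting, since the vials carry the acquisition date and time.

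**Cost.** No additional tissue is needed and pairs can still share an array. A code list must be kept and independently checked, because a coding error would reverse that patient's direction of change, which matters with 10 pairs. Recoding frozen vials is a small extra task for someone outside the blotting laboratory. Masking will be imperfect if treated tissue looks different, for example through necrosis; reporting rejections by time point would at least make uneven exclusion visible.
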